9.2.3 Case Report Forms

An investigator is required to prepare and maintain adequate and accurate case histories designed to record all observations and other data pertinent to the investigation on each individual treated or entered as a control in the investigation. Data that are derived from source documents and reported on the CRF must be consistent with the source documents or the discrepancies must be explained. Additional clinical information may be collected and analyzed in an effort to enhance understanding of product safety. CRFs may be requested for AEs and/or laboratory abnormalities that are reported or identified during the course of the study.

For sites using the BMS electronic data capture tool, electronic CRFs will be prepared for all data collection fields except for fields specific to SAEs and pregnancy, which will be reported on the paper or electronic SAE form and Pregnancy Surveillance form, respectively. If electronic SAE form is not available, a paper SAE form can be used. Spaces may be left blank only in those circumstances permitted by study-specific CRF completion guidelines provided by BMS.

The confidentiality of records that could identify subjects must be protected, respecting the privacy and confidentiality rules in accordance with the applicable regulatory requirement(s).

The investigator will maintain a signature sheet to document signatures and initials of all persons authorized to make entries and/or corrections on CRFs.

The completed CRF, SAE/pregnancy CRFs, must be promptly reviewed, signed, and dated by the investigator or qualified physician who is a subinvestigator and who is delegated this task on the

Delegation of Authority Form. Subinvestigators in Japan may not be delegated the CRF approval task. For electronic CRFs, review and approval/signature is completed electronically through the BMS electronic data capture tool. The investigator must retain a copy of the CRFs including records of the changes and corrections.

Each individual electronically signing electronic CRFs must meet BMS training requirements and must only access the BMS electronic data capture tool using the unique user account provided by BMS. User accounts are not to be shared or reassigned to other individuals.

9.3 Clinical Study Report and Publications

A Signatory Investigator must be selected to sign the clinical study report.

For this protocol, the Signatory Investigator will be selected as appropriate based on the following criteria:

- External Principal Investigator designated at protocol development
- National Coordinating Investigator
- Subject recruitment (eg, among the top quartile of enrollers)
- Involvement in trial design
- Regional representation (eg, among top quartile of enrollers from a specified region or country)

The data collected during this study are confidential and proprietary to BMS. Any publications or abstracts arising from this study must adhere to the publication requirements set forth in the clinical trial agreement (CTA) governing [Study site or Investigator] participation in the study. These requirements include, but are not limited to, submitting proposed publications to BMS at the earliest practicable time prior to submission or presentation and otherwise within the time period set forth in the CTA.

10 GLOSSARY OF TERMS

Term	Definition
Complete Abstinence	Complete Abstinence is defined as complete avoidance of heterosexual intercourse and is an acceptable form of contraception for all study drugs. This also means that abstinence is the preferred and usual lifestyle of the patient. This does not mean periodic abstinence (e.g., calendar, ovulation, symptothermal, profession of abstinence for entry into a clinical trial, post-ovulation methods) and withdrawal, which are not acceptable methods of contraception. Women must continue to have pregnancy tests. Acceptable alternate methods of highly or less effective contraception's must be discussed in the event that the subject chooses to forego complete abstinence.

11 LIST OF ABBREVIATIONS

Term	Definition
ACTH	adrenocorticotrophic hormone
ADA	anti-drug antibodies
AE(s)	adverse event(s)
AIDS	Acquired Immunodeficiency Syndrome
ALT	alanine aminotransferase
ALP	Alkaline phosphatase
ANC	absolute neutrophil count
AST	aspartate aminotransferase
β-HCG	beta-human chorionic gonadotrophin
BA/BE	bioavailability/bioequivalence
BMS	Bristol-Myers Squibb
BOR	Best Overall Response
BP	blood pressure
BSA	body surface area
BUN	blood urea nitrogen
Ca ⁺⁺	calcium
CBC	complete blood count
CFR	Code of Federal Regulations
CI	confidence interval
CL	clearance
CNS	central nervous system
CR	complete response
CrCl	creatinine clearance
CRF	Case Report Form, paper or electronic
CTA	clinical trial agreement
CTCAE	Common Terminology Criteria for Adverse Events
CTLA 4	Cytotoxic T lymphocyte associated antigen 4
%CV%	geometric mean
DILI	drug-induced liver injury

Term	Definition
dL	deciliter
DMC	Data Monitoring Committee
DNA	deoxyribonucleic acid
DTIC	Dacarbazine
EANO	European Association of Neuro-Oncology
EC	ethics committee
ECG	electrocardiogram
ECOG	Eastern Cooperative Oncology Group
eCRF	electronic case report form
EDC	electronic data capture
eg	exempli gratia (for example)
eGFR	estimated glomerular filtration rate
EGFR	epidermal growth factor receptor
ELISA	enzyme-linked immunosorbent assay
EQ-VAS	EuroQol visual analog scale
EORTC	European Organization for Research and Treatment of Cancer
ESR	expedited safety report
FDA	Food and Drug Administration
FFPE	Formalin-Fixed, Paraffin-Embedded
FLAIR	fast fluid-attenuated inversion recovery
FSH	follicle stimulating hormone
GBM	glioblastoma
GCP	Good Clinical Practice
GFR	glomerular filtration rate
GI	gastrointestinal
Gy	gray (radiotherapy dose)
HBsAg	hepatitis B surface antigen
HBV	hepatitis B virus
HCG	human chorionic gonadotropin
HCV	hepatitis C virus

Term	Definition
HCV-RNA	hepatitis C virus-ribonucleic acid
HIPAA	Health Insurance Portability and Accountability Act
HIV	Human Immunodeficiency Virus
HR	heart rate
HrQoL	health-related quality of life
HRT	hormone replacement therapy
IB	investigator brochure
ICD	Implantable Cardioverter Defibrillator
ICF	informed consent form
ICH	International Conference on Harmonisation
ICOS	increased activation markers
ie	id est (that is)
IEC	Independent Ethics Committee
Ig	Immunoglobulin
IHC	immunohistochemistry
imAEs	immune-mediated adverse events
IMP	investigational medicinal products
IND	Investigational New Drug Exemption
I-O	immuno-oncology
IP	investigational product
iRANO	Immune Radiologic Assessment in Neuro-Oncology
IRB	Institutional Review Board
IRC	Independent Radiology Review Committee
IU	International Unit
IUDs	Intrauterine devices
IV	intravenous
IVRS	Interactive voice response system
ITIM	Immunoreceptor tyrosine inhibitory motif
ITSM	Immunoreceptor tyrosine-based switch motif
K+	potassium

Term	Definition
kg	kilogram
KPS	Karnofsky Performance Status
LDH	lactate dehydrogenase
LFT	liver function test
mAbs	monoclonal antibodies
mg	milligram
Mg/kg	Milligram per kilogram
Mg ⁺⁺	magnesium
MGMT	tumor O-6-methylguanine DNA methyltransferase
mL	milliliter
MRI	Magnetic Resonance Imaging
MST	Medical safety team
MTD	maximum tolerated dose
µg	microgram
N	number of subjects or observations
N	nivolumab (BMS-936558)
Na ⁺	sodium
NANO	Neurologic Assessment in Neuro-Oncology
N/A	not applicable
NCCN	National Comprehensive Cancer Network
NCI	National Cancer Institute
NE	Not evaluable
NIMP	non-investigational medicinal products
NSCLC	non-small cell lung carcinoma
O ₂	Oxygen
OS	overall survival
PBMC	Peripheral blood mononuclear cell
PCR	polymerase chain reaction
PD	pharmacodynamics
PD	progressive disease

Term	Definition
PD-1	Programmed cell death protein 1
PD-L 1	Programmed cell death ligand 1
PFS	Progression-free survival
PID	Patient identifier
PK	pharmacokinetics
PO	per os (by mouth route of administration)
PPK	population pharmacokinetics
PR	partial response
PVC	polyvinyl chloride
QD	once a day
QLQ-C30	European Organization for Research and Treatment of Care General Cancer Module
QLQ-BN20	European Organization for Research and Treatment of Cancer - Brain Cancer Module
QOL	Quality of life
QxW	Every x weeks
RANO	Radiologic Assessment in Neuro-Oncology
RCC	Renal cell carcinoma
RNA	ribonucleic acid
RR	respiratory rate
RT	radiation therapy
RT-PCR	reverse transcription polymerase
SAE(s)	serious adverse event(s)
SAP	statistical analysis plan
SD	stable disease
SmPC	summary of product characteristics
SNP	single nucleotide polymorphism
SOC	standard of care
SOP	Standard Operating Procedures
T1/2	Geometric elimination half-life
TCR	T cell receptor

Term	Definition
TIL	tumor infiltrating lymphocytes
TMB	tumor mutational burden
TMZ	Temozolomide
TSH	thyroid stimulating hormone
µg	microgram
ULN	upper limit of normal
VAS	visual analogue scale
V _{ss}	volume of distribution at steady state
w	week
WBC	white blood cell
WHO	World Health Organization
WOCBP	women of childbearing potential

UNACCEPTABLE METHODS OF CONTRACEPTION

- 1) Periodic abstinence (calendar, symptothermal, post-ovulation methods)
- 2) Withdrawal (coitus interruptus)
- 3) Spermicide only
- 4) Lactation amenorrhea method (LAM)

2 STUDY DESCRIPTION

2.1 Study Design

This study will enroll subjects with newly-diagnosed glioblastoma (GBM), following surgical resection of the tumor. After informed consent is obtained, subjects will enter the screening phase. Tumor tissue will be evaluated for MGMT methylation by a central laboratory assay.

[REDACTED]

Post-operative baseline MRI following consensus recommendations, must be obtained prior to randomization. It is strongly recommended that this scan be obtained < 72hrs or > 14 days post-surgery in order to minimize artifact. There is no requirement that this baseline scan be performed on a “qualified” machine (a qualified MRI is one that meets the Imaging Manual specifications and has been validated with the required phantom scan). If a post-operative MRI is not available, a high-quality, contrast-enhanced CT scan may be performed initially, but in this case a contrast-enhanced MRI must be performed prior to randomization (> 2 weeks post-operative preferred).

Subjects with a central laboratory result of **un**methyated MGMT may continue in the **screening phase**, in which eligibility for randomization will be documented and baseline demographic and disease information submitted

[figure not shown]
When ready to begin study treatment, subjects will proceed to the **treatment phase** of the study. The treatment phase will consist of an induction phase (chemoradiation therapy) followed by 4 weeks break and maintenance temozolomide therapy; for details, see Figure 2.1-1. All subjects who enter the treatment phase, i.e., all randomized subjects, will be followed for safety and tolerability, tumor progression and survival. A contrast-enhanced MRI should be performed 4 weeks (± 7 days) after completing radiation therapy, then every 8 weeks (± 7 days) until progression regardless of treatment schedule or dose delays. Tumor progression will be assessed using Radiologic Assessment in Neuro-Oncology criteria (RANO). Additional assessments will be performed for cognitive function, neurologic function, biomarkers and patient-reported quality of life outcomes.

After cessation of study treatment for any reason, all randomized subjects will enter a **follow up** phase. In the short-term, visits are defined for reporting of treatment-related adverse events. All subjects in whom disease progression had not been detected at the time study treatment is stopped will be followed closely for progression with contrast enhanced MRI every 8 weeks (± 7 days) until progression. After progression, subjects **MUST** be followed for survival (primary endpoint); subsequent treatments will be reported.

Baseline and all subsequent scans will be submitted to a blinded independent radiology review committee (BIRC) for archiving, once the subject is randomized and throughout the study period.

A Data Monitoring Committee (DMC) will meet regularly during the study to ensure that subject safety is carefully monitored.

Figure 2.1-1: Study Design Schematic

2.1.1 Screening Phase

Subjects will provide consent for enrollment and tumor submission in the peri-operative period, so that MGMT status can be determined, but consent for randomization and study treatment should

be deferred until MGMT unmethylated status and eligibility is established. The clinical circumstances should be considered with respect to the timing of consent.

Following informed consent, subjects with histologic diagnosis of GBM and no evident exclusions will be enrolled via a call to an IVRS system, in order to obtain a subject number, after which tumor tissue will be submitted to the central laboratory. For details, see a centralized tumor tissue assay for MGMT is required for randomization. Therefore, the tumor sample should be submitted as soon as possible.

Eligibility will be established and baseline information submitted for subjects with a central laboratory result of unmethylated MGMT. A subject cannot be randomized until the result of the central laboratory MGMT is entered into the IVRS. Subjects without a confirmed result of unmethylated MGMT will be considered screen failures and will not be eligible for randomization. If the assay result is methylated or indeterminate MGMT, they may be enrolled onto another BMS study (if available) based on the same MGMT assay.

It is expected that corticosteroid therapy will be tapered to the maximum extent possible during this phase. Subjects who cannot tolerate tapering of steroids to < 20mg prednisone or < 3mg dexamethasone per day (or equivalent) are not eligible for randomization.

RT should begin within 42 days of surgical resection, but may be delayed if clinically required. Typically, the time from screening procedure to treatment should not exceed 28 days, but may be longer if clinically indicated. If repeat resection to improve tumor control is performed for newly-diagnosed GBM prior to any other therapy (e.g., upon referral to research site), the 42-day interval should restart at the time of this second surgery and a new post-operative MRI must be performed.

2.2 Treatment Assignment

After informed consent has been obtained, the subject must be enrolled into the study by calling an IVRS to obtain the subject number. Every subject that signs the informed consent form must be assigned a subject number in IVRS. The investigator or designee will register the subject for enrollment by following the enrollment procedures established by BMS. The following information is required for enrollment:

- Date that informed consent was obtained
- Date of birth of subject
- Gender (at birth) of subject

CA209498 is a randomized study. Central lab confirmation of MGMT un-methylated status must be received prior to the IVRS randomization call. Once enrolled in IVRS, enrolled subjects who meet all eligibility criteria, and are clinically ready to begin treatment, will be randomized through the IVRS. The following information is required for randomization:

- Subject number
- Date of birth of subject

- Extent of tumor resection: Complete or Partial

Subjects meeting all eligibility criteria will be randomized in a 1:1 ratio to receive radiotherapy + nivolumab (RT+ nivolumab) or radiotherapy + temozolomide (RT + TMZ). MGMT methylation status will be transferred from the testing laboratory to the IVRS database.

The exact procedures for using the IVRS are detailed in the IVRS manual.

2.3 Blinding and Unblinding

Not applicable. This is an open-label study.

2.4 Protocol Amendments

This SAP (version 3.0) incorporates the following amendments:

Table 2.4-1: Protocol Amendments

Amendment	Date of Issue	Summary of Major Changes
Revised Protocol 01 (Incorporate Amendment 03)	12-Jan-2016	Added exclusion for subjects with prior hypersensitivity to dacarbazine (DTIC); Added definition of Suspected, Unexpected Serious Adverse Event Reaction (SUSAR) and statement of SUSAR reporting responsibilities.
Revised Protocol 02 (Incorporates Amendment 04)	24-Feb-016	Corrected the temozolomide dose modification guidance during maintenance temozolomide dosing; modified nivolumab dose delay and discontinuation criteria
Revised Protocol 03 (Incorporates Amendment 06 and Administrative Letter 01)	04-May-2016	Major changes implemented in this Amendment include 
 1) Eligibility criteria 
 a) Add exclusion for Gliadel® wafer b) Permit baseline MRI to be performed up to 72 hours postoperatively. If only CT is available, an MRI must be obtained prior to randomization. c) Modified language for women of child-bearing potential 2) Modify cutoff values used to define complete vs partial resection for purposes of randomization

Table 2.4-1: Protocol Amendments

Amendment	Date of Issue	Summary of Major Changes

Revised Protocol 04 (Incorporates amendment 08)
	
09-Nov-2016
	
4) Update language throughout to conform with the Health Authority requests
 
[REDACTED]
 
6) Clarify treatment plan
 
a) Insert guidance for radiation therapy as an appendix (referenced in Section 3.1.2.2)
 
b) Switch from 240mg Q2 wk to 480mg Q4 wk after 8 doses (rather than 16 weeks)
 
c) Aligned start of nivolumab and start of temozolomide to within 7 days of randomization
 
d) Clarify that TMZ dosing is per institutional standards and update dose modification table to conform with SmPC


Revised Protocol 05
	
15-Nov-2017
	
This amendment updates the nivolumab clinical information in GBM and safety management algorithms as a result of most recent version of the Investigator Brochure (version 15). The amendment also clarifies several items as well as corrects minor errors.
 
[REDACTED]
 
 Renal, Pulmonary, Hepatic, and Skin safety management algorithms revised based on IBv.15 
Time windows and technical descriptions around assessments and administration schedule have been added or expanded to allow for flexibility at the site level while not affecting the conduct or the analysis of the data.

Major changes included are:
		

Table 2.4-1: Protocol Amendments

Amendment	Date of Issue	Summary of Major Changes
(Incorporates Administrative Letters 04 and 05 and amendment 09)		1) Removal of the interim analysis for superiority of the primary endpoint of OS. 2) Addition of a secondary endpoint that evaluated, in newly diagnosed, unmethylated MGMT GBM, any relationship between OS or PFS and TMB in the RT + nivolumab arm compared to the RT + TMZ control arm.

2.5 Data monitoring Committee

An independent Data Monitoring Committee (DMC) has been established to provide oversight of safety and efficacy considerations, study conduct, and risk-benefit ratio. Following review, the DMC will recommend continuation, modification, or discontinuation of this study based on reported safety and efficacy data. Details of DMC responsibilities and procedures are specified in the DMC charter¹. Representatives of the Sponsor will serve only as coordinators of the committee, without having full member responsibilities or privileges. In addition, the Sponsor will independently review safety data in a blinded manner to ensure that any safety issues are identified and addressed.

3 OBJECTIVES

3.1 Primary

To compare OS of nivolumab in addition to radiation therapy versus temozolomide in addition to radiation therapy in subjects with newly diagnosed GBM with unmethylated MGMT tumors after surgical resection

3.2 Secondary

- To compare investigator-assessed PFS of RT + nivolumab versus RT + TMZ
- To estimate the OS rate at 24 months (OS[24]) of RT + nivolumab versus RT + TMZ
- To evaluate, in newly diagnosed, unmethylated MGMT GBM, any relationship between OS or PFS and tumor mutational burden (TMB) in the RT+nivolumab arm compared to the RT+TMZ control arm

[REDACTED]

[REDACTED]

[REDACTED]

[REDACTED]

[REDACTED]

[REDACTED]

[REDACTED]

[REDACTED]

[REDACTED]

4 ENDPOINTS

4.1 Primary

The primary endpoint is OS. OS is defined as the time between the date of randomization and the date of death due to any cause. A subject who has not died will be censored at the last known alive date.

4.2 Secondary

[figure not shown]
4.2.1 *Progression Free Survival*

PFS is defined as the time from randomization to the date of the first documented tumor progression or death due to any cause. Subjects who did not have disease progression or who did not die will be censored at the date of last tumor assessment. Subjects who did not have any on study tumor assessment and did not have tumor progression or die will be censored at the randomization date. Subjects who started any subsequent anti-cancer therapy without a prior reported progression will be censored at the last tumor assessment prior to initiation of the subsequent anti-cancer therapy. Subjects who had surgical resection post start of study treatment will be censored at the last tumor assessment date prior to initiation of surgical resection. PFS will be determined by investigator reported response based on RANO criteria

The progression free survival rate at time T is defined as the probability that a subject has not progressed and is alive at time T following randomization.

Censoring rules for the primary analysis of PFS are presented in Figure 4.2.1-1 Alternate censoring rules for sensitivity analyses are specified in Section 7.5.3.2.

Figure 4.2.1-1: Graphic Display of PFS Primary Definition

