5.4.1 Suspected Progression

In order to distinguish potential treatment effects (or “pseudoprogession”) from progressive disease and thus to minimize premature discontinuation of nivolumab or temozolomide, subjects who initially meet radiologic criteria for disease progression, but are tolerating study drug, may continue receiving study drug until confirmation of progression with an MRI performed approximately 8 weeks later. If possible, MRI perfusion images should also be obtained. If a determination cannot be made after an 8 week interval, then treatment may continue until either progression is confirmed or regression is observed, consistent with either pseudoprogession or

immune-treatment effect. Consultation with the BMS Medical Monitor is recommended but not required.

Confirmation of progression is mandatory if recurrence occurs within 12 weeks of completion of RT. Suspected disease progression within 12 weeks after the end of RT must be confirmed by subsequent MRI performed within 8 weeks after the initial radiological assessment of progression. Prior to 12 weeks after RT, progression can only be defined using diagnostic imaging if there is new enhancement outside of the radiation field (beyond the high-dose region or 80% isodose line) or if there is unequivocal evidence of viable tumor on histopathologic sampling.³⁹ Note: in the absence of radiographic or histologic confirmation of progression, clinical decline alone is not sufficient for definition of progressive disease.

If the follow-up assessment confirms that progression has occurred, the date of progression will be the date at which progression was first determined. If the follow-up assessment does not confirm progression, then the original time point response will be assessed as SD.

[REDACTED]

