7.4.3.3 Subsequent Cancer Therapy

Number and percentage of subjects receiving subsequent cancer therapies will be summarized. Categories include:

- Subsequent systemic therapy
- Subsequent surgery for treatment of tumors (restricted to tumor resection)
- Subsequent radiotherapy for treatment of tumors

A by-subject listing of subsequent cancer therapy will also be produced for all randomized subjects.

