7.5.3.2 Sensitivity Analysis

Sensitivity analyses of PFS will also be performed using the following modification:

- 1) PFS accounting for assessment after subsequent therapy. It will be defined similar to the primary definition except that events (progression or death) and tumor assessments that occurred after subsequent anticancer therapy or diagnostic surgical resection will be taken into account (see censoring scheme 1 for sensitivity analysis in Figure 7.5.3.2-1).

Figure 7.5.3.2-1: Graphic Display of PFS Accounting for Assessment after Subsequent Therapy

- 2) PFS not considering clinical progression as event: It will be defined same as the primary definition except not considering clinical progression as progression event.
- 3) PFS accounting for assessment after subsequent therapy and not counting clinical progression as event: It will be defined same as sensitivity analysis #1 defined above except not considering clinical progression as progression event.

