		
Section 7.2.2 Relevant Protocol Deviations: new deviation “Subjects without baseline MRI scan”.
 
[REDACTED]
 
Section 7.3.1 Subject Disposition: Analysis population is specified; description of listings is updated to be compliant with the CRF and support the tables.
 
[REDACTED]
 
Section 7.3.4 Prior Therapy: Summaries of agents by name and by ATC class are specified.
 
Section 7.4.1 Administration of Study Therapy: The denominator for duration of treatment in months is corrected to 30.4375; definition of the last cycle length is corrected; terms “Dose Intensity”, “Relative Dose intensity” and the definitions are made compliant; populations for exposure analysis are restricted to subjects treated with a particular drug; definition of TMZ Dose (mg/m2) is corrected to be defined via BSA instead of weight; the following analyses for TMZ maintenance phase is removed: Cycles of treatment, Number of subjects completing 6 cycles; structure of the section is improved.
 
Section 7.4.2 Modifications of Study Therapy: Populations for exposure analysis is restricted to subjects treated with a particular drug.
 
Section 7.4.2.1 Nivolumab Dose delays: Definition of a delayed dose is added.
 
Section 7.4.2.3 Radiotherapy and Temozolomide is split to 7.4.2.3 Temozolomide Dose Modifications and 7.4.2.4 Missing Radiotherapy for compliance of the analyses with the CRF
 
[REDACTED]
 
Section 7.4.3.3 Subsequent Cancer Therapy is moved from 7.5. Efficacy; subsequent surgeries for “Other” reason and with a specification which includes ‘RESECTION’ will be accounted for subsequent therapy.
 
Section 7.5. Efficacy: Use of the stratification factor is specified.

Table 10-1: Document History

Version Number	Author	Description

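### The readable primary PFS text censors every subject resected after start of treatment, without the no-earlier-progression condition that the neighbouring therapy sentence carries

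*SAP*

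**What the plan says.** SAP 4.2.1 defines the endpoint: "PFS is defined as the time from randomization to the date of the first documented tumor progression or death due to any cause". Two censoring sentences then stand side by side. On subsequent therapy: "Subjects who started any subsequent anti-cancer therapy without a prior reported progression will be censored at the last tumor assessment" before that therapy began. On surgery: "Subjects who had surgical resection post start of study treatment will be censored at the last tumor assessment date prior to initiation of surgical resection". Protocol 8.3.2 and the synopsis repeat the surgery sentence, also without a condition. The SAP adds: "Censoring rules for the primary analysis of PFS are presented in Figure 4.2.1-1". That figure is not readable in the text available.

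Other places bear on the intent:

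- SAP 7.4.3.3 lists tumor resection among subsequent cancer therapies. The version 3.0 change note says that certain surgeries specified as resections "will be accounted for subsequent therapy".
- Sensitivity analysis 1 in SAP 7.5.3.2 is "defined similar to the primary definition except that events (progression or death) and tumor assessments that occurred after subsequent anticancer therapy or diagnostic surgical resection" are counted.
- SAP 7.5.3.1 tests PFS only if OS is positive. Its list of PFS censoring reasons has no separate entry for resection.

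Protocol 5.4.1 limits how early progression can be called: "Prior to 12 weeks after RT, progression can only be defined using diagnostic imaging if there is new enhancement outside of the radiation field", or if histology shows unequivocal viable tumor. A progression confirmed at follow-up is dated to when it was first determined; one that is not confirmed is scored as stable disease.

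**The concern.** Take a subject whose scan documents progression and who is then resected. Under the definition this is an event on the scan date. Under the literal resection sentence the same subject is censored, typically on that same date, because the progression scan is the last assessment before surgery. The two rules cannot both apply.

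PFS is the only secondary endpoint that is formally tested. If resections were equally common in the arms, events would be lost and the PFS medians lengthened, with no bias in the hazard ratio. If they were unequal, the hazard ratio would move in favour of the arm resected more often.

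A second, smaller problem would survive the repair. Suppose a scan within 12 weeks of radiotherapy raises suspicion and the resection specimen supplies the first proof. No progression had been reported before surgery, so the resection sentence censors at that scan. The dating rule in Protocol 5.4.1 may instead place an event on that scan, but it speaks of a follow-up assessment in a passage about repeat MRI and does not say whether a specimen qualifies.

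**Working it through.** **The plan's own figures.** The documents give no event count or median for PFS and no resection rate. The OS design reproduces: 4 × (1.960 + 1.282)² / (ln 0.72)² = 42.03 / 0.1079 = 389.5, so 390 deaths; critical HR = exp(−2 × 1.96 / √390) = 0.82. Neither figure is touched by this point.

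**Inputs from the documents.** 550 subjects randomized 1:1; 10 months' accrual; analysis at 33 months; radiotherapy starting within 7 days of randomization; MRI 4 weeks after radiotherapy, then every 8 weeks (± 7 days).

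**Assumed inputs.** Exponential time to first event, median 6 months in both arms; median survival after progression 7 months; 6 weeks of radiotherapy (the protocol says 6–7); resected shares of 5, 10 or 20% of detected progressions. Simulation on these inputs gives about 525 PFS events, of which 9.7 to 27.9% are deaths (middle case 18.7%).

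**Detected progressions.** 525 × (1 − 0.097) = 474; 525 × (1 − 0.187) = 427; 525 × (1 − 0.279) ≈ 378.

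**Literal rule: events lost.** Detected progressions × share resected:

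| Share resected, each arm | Events lost |
|---|---|
| 5% | 19–24 |
| 10% | 38–47 |
| 20% | 76–95 |

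With 10% in both arms the simulated HR stays at 1.00 and median PFS rises from 6.7 to 7.5 months.

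**Literal rule: HR when the true HR is 1.** Relabelling a share of progressions while keeping deaths gives approximately HR = (1 − p·x) / (1 − p·y), with p the progression share of events (0.813 in the middle case), x the resected share on nivolumab and y on temozolomide.

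- 20% vs 10%: (1 − 0.1626) / (1 − 0.0813) = 0.837 / 0.919 = 0.91. Simulated: 0.915, about 0.92.
- 10% vs 5%: 0.919 / 0.959 = 0.96. Simulated: 0.96.
- With the shares reversed, the simulated values are 1.10 and 1.05.
- If no events were deaths (p = 1), 20% vs 10% would give 0.80 / 0.90 = 0.89.

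**Condition added: what remains.** Only early progressions first proven by the specimen are at issue. In the simulation about 25% of detected progressions appear at the scan 4 weeks after radiotherapy, so the pool is 0.25 × 378 to 0.25 × 474, or about 95 to 119.

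| Share of these resected first | Events lost |
|---|---|
| 5% | 5–6 |
| 10% | 9–12 |
| 20% | 19–24 |

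The same approximation with p × 0.25 = 0.203 gives, for 20% vs 10%, (1 − 0.0407) / (1 − 0.0203) = 0.98, and for 10% vs 5%, (1 − 0.0203) / (1 − 0.0102) = 0.99.

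**The case against.** The best defence is that the plan as a whole already implies the condition. PFS runs to the first documented progression, so a later operation should not undo it. Sensitivity analysis 1 differs from the primary only by adding what happens after therapy or resection, which presupposes that the primary counts what came before. Resection is classed as subsequent therapy, and the therapy sentence has the condition. The programmer would also have Figure 4.2.1-1. All of this stands as evidence of intent, and it is why the literal figures above describe a risk and not an expected result. It does not remove the conflict in the wording, which appears in three places.

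Four stronger readings are tempting and are not supported:

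- *That the analysis will in fact censor documented progressions.* The figure cannot be read here, so this is a conflict to reconcile and not a shown programming error.
- *That the rule favours nivolumab.* Re-operation to tell treatment effect from progression is mentioned only in the nivolumab section (Protocol 4.5.1.6), but Table 5.1-2 foresees resection at progression in both arms, and no rate by arm is given.
- *That progressions at the second scan also belong to the early problem.* Including them raises the share from 25% to about 40%, but footnote a of Table 5.1-2 recommends that scan at least 84 days after radiotherapy, which puts it largely outside the 12-week window.
- *That the plan has no way to classify a specimen.* The RANO section to which Protocol 8.3.2 refers is not visible and may say more.

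It is also fair that the term used in SAP 7.5.3.2 (diagnostic resection) and the missing table row are editorial. Resection censorings may be counted under subsequent therapy, and SAP 7.4.3.3 already summarizes resections.

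**Conclusion.** The point holds as a wording defect in a stated rule: on the readable text, the resection sentence contradicts the PFS definition for anyone who progresses and is then resected. It is probably an omission. The specimen-proven case within 12 weeks of radiotherapy is a real but narrow ambiguity.

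The consequence is limited. OS is unaffected, PFS is tested only after a positive OS result, and sensitivity analysis 1 counts events after resection, although it is not the tested analysis. An HR of about 0.92 requires both the literal reading and an assumed 20% versus 10% imbalance. With the condition in place, the distortion is about 0.98 to 0.99 under the same twofold imbalances. All sizes rest on assumed resection shares and an assumed 6-month median. Severity: minor to should-fix.

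**What to change.** 1. Add to the resection sentence in SAP 4.2.1, Protocol 8.3.2 and the synopsis the same condition that the subsequent-therapy sentence carries, namely that no progression was reported beforehand. Confirm that Figure 4.2.1-1 agrees.
2. Reconcile that sentence with Protocol 5.4.1 and the RANO section. The SAP should state whether progression confirmed by a resection specimen is a PFS event, and that any such event is dated by the existing 5.4.1 rule. A new rule that dates events to surgery is not needed.
3. Optional and editorial: use one term for resection in SAP 4.2.1 and 7.5.3.2, and show censoring for resection by arm in the SAP 7.5.3.1 table.

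Sensitivity analysis 1 can otherwise stay as it is. The cost is a clause in three places, one clarifying statement, and at most one term, one table row and minor programming. No new data or subjects are needed; the schedule already asks for tissue when resection is done at progression or suspected progression.
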